2. SYNOPSIS

Name of Sponsor/Company: EyeQue Corporation

Name of Investigational Device: EyeQue VisionCheck

Title of Study: A clinical validation study to evaluate the performance of a hand-held device supported by a mobile application compared with standard eye care diagnostic devices in measuring refractive error of the eye

Study Number: EYEQUE-001

Study center(s): 1

Studied period (years):

Estimated date first patient enrolled: Q2 2019

Estimated date last patient completed: Q3 2019

Objectives:

Primary:

• The primary objective of this study is to determine whether EyeQue VisionCheck is statistically non-inferior to the phoropter as assessed by best corrected visual acuity (BCVA) for each eye independently, measured using trial lens frames that correct the refractive error measured by each device, for the age stratum 45 through 65 years.

Secondary:

The secondary objectives include:

- Assessing similarity of refraction values (sphere, cylinder, axis) from the EyeQue VisionCheck compared with the phoropter through comparative plots and Pearson correlations
- Determining whether EyeQue VisionCheck is statistically non-inferior to the autorefractor as assessed by BCVA measured using trial lens frames that correct the refractive error measured by each device
- Assessing similarity of refraction values (sphere, cylinder, axis) from the EyeQue VisionCheck compared with the autorefractor through comparative plots and Pearson correlations
- Determining whether EyeQue VisionCheck is statistically non-inferior to the phoropter as assessed by BCVA measured using trial lens frames that correct the refractive error measured by each device, for the age stratum 30 through 65 years.

Exploratory:

• The exploratory objective of this study is to assess subject preference among the 3 trial lens frames that correct the refractive error measured by the EyeQue VisionCheck, phoropter, and autorefractor.

Safety:

• To evaluate the safety of EyeQue VisionCheck compared with the phoropter and the autorefractor

Study design: This is a single-center, open-label, prospective study in healthy volunteers desiring refraction for correction of visual acuity to compare the EyeQue VisionCheck with the phoropter and autorefractor.

Approximately 200 subjects will be enrolled in this study to achieve a minimum of 100 evaluable subjects. Subjects will be enrolled to obtain a population of approximately 35% in the age range of 30 through 44 years and approximately 65% in the age range of 45 through 65 years. Subjects will be screened for study participation and, if enrolled, will complete the testing procedures at the same visit. Subjects will not undergo any study-specific screening or testing procedures until written informed consent is obtained. A subject will be enrolled in the study after confirming that the subject has met all of the inclusion criteria and none of the exclusion criteria.

Screening procedures

The subject will complete the following assessments and procedures at Screening to confirm eligibility:

- demographics/medical history/concomitant medication review,
- slit-lamp biomicroscopy,
- laser retinal scan or fundoscopy,
- optical coherence tomography (OCT) (retina and anterior chamber),
- tonometry (non contact),
- Ishihara color test,
- cover test,
- retinoscopy
- phoropter refraction, and
- visual acuity with phoropter correction.

During the OCT and laser retinal scan/fundoscopy, images will be taken of the retina, anterior chamber, and fundus. All eye procedures will be completed without dilation using standard procedures.

Retinoscopy will be used as a basis for further refinement by phoropter refraction. Refraction values (sphere, cylinder, axis) for oculus dexter (OD, right eye) and oculus sinister (OS, left eye) will be recorded for each subject using the phoropter. These values will be used to adjust the lenses in the phoropter while the subject is looking through the device at an Early Treatment Diabetic Retinopathy Study (ETDRS) eye chart to determine BCVA, as subjects are eligible to participate in the study only if their vision (oculus uterque [OU]; both eyes) can be corrected to 20/20 (logarithm of the minimum angle of resolution [LogMAR] 0.0).

The Screening procedures will be used to confirm that the subject does not have an exclusionary diagnosis (see exclusion criteria below).

Testing procedures

Once eligibility is confirmed, the subject will be enrolled and proceed with study testing procedures. The refraction values (sphere, cylinder, axis) for each subject (OD and OS) will be assessed using 2 additional devices: autorefractor and the EyeQue VisionCheck. Subjects will be assessed with the autorefractor using standard device methodology. The refraction values generated from the EyeQue VisionCheck, the autorefractor and the phoropter (during screening) will be used to prepare 3 sets of trial lens frames. Pupillary distance, measured using the autorefractor, will be recorded for all subjects and will be used for preparation of trial lens frames.

All subjects will be trained on how to use the EyeQue VisionCheck device prior to initiating testing. In order to obtain refraction values using the EyeQue VisionCheck, the subject will be required to take 1 practice test followed by a minimum of 3 saved tests for each eye using the EyeQue VisionCheck device and mobile application (app). After completion of a set of tests (1 test for each eye), the subject may elect to save or discard that set of tests. They may choose to discard for any reason which may include not following instruction, pressing the wrong button in error, etc. Each test consists of the subject looking through the VisionCheck device and using the app controls to fully overlap red and green bars at 9 different angles. After completion of all tests (1 practice test and 3 saved tests with each eye), the refraction values will be displayed on the mobile app. These values will be used for preparation of the trial lens frames. If the EyeQue system determines that the overall test results are unreliable, subjects may have to complete 3 additional tests per eye before the system may be able to provide refraction values. Subjects will not be allowed to complete more than 6 saved tests and 1 practice test with each eye. If the EyeQue system determines that the overall test results are unreliable, no values will be provided.

After collection of refraction values from each device (phoropter, autorefractor, and EyeQue VisionCheck), the 3 trial lens frames will be prepared and given to the subject in a masked fashion. Best corrected visual acuity will be assessed using the ETDRS eye chart. For each subject, BCVA LogMAR scores will be collected for OD, OS, and OU for each of the 3 trial lens frames. Subjects will also be asked a question regarding overall satisfaction with visual acuity using each of the 3 trial lens frames. Subjects will be monitored for adverse events (AEs) and adverse device effects (ADEs) during the study.

Number of subjects (planned): Approximately 200 subjects will be enrolled in this study to achieve a minimum of 100 evaluable subjects. An initial cohort of 39 subjects will be excluded from the analysis populations due to a software error identified in the EyeQue app that has since been corrected; therefore, approximately 160 additional subjects will be enrolled in the study. Subjects will be enrolled to obtain a population of approximately 35% in the age range of 30 through 44 years and approximately 65% in the age range of 45 through 65 years.

Diagnosis and main criteria for inclusion: Inclusion criteria:

1. Male or Female

- 2. Age 30 through 65 years at the time of consent
- 3. Binocular vision
- 4. Subject desires refraction for correction of visual acuity and vision (OU) can be corrected to 20/20 (LogMAR 0.0)
- 5. Willing and able to give informed consent and follow all study procedures and requirements
- 6. Ability to speak and understand the English language

Exclusion criteria:

- 1. Spherical correction > +8 or < -10
- 2. Using anticholinergic medications (including first-generation antihistamines) or other medications known to affect visual acuity within the greater of 3 days or 5 half-lives prior to enrolling in this study
- 3. Using an investigational drug or approved therapy for investigational use within the greater of 3 days or 5 half-lives prior to enrolling in this study
- 4. Has initiated any new medication in the past 2 weeks that, in the best medical judgment of the investigator, would impact their participation in the study or ability to use the EyeQue VisionCheck device
- 5. Eye disease, including but not limited to:
 - Glaucoma (\geq 22 mmHg intraocular pressure)
 - Cataracts (≥ 1+ nuclear sclerotic cataract, ≥ 1+ cortical, posterior subcapsular cataract [any grade using the Lens Opacities Classification System III])
 - Macular degeneration (retinal pigmented epithelium mottling and/or any drusen within 500 µm of macula)
 - Eye infection (corneal ulcer, corneal infiltrates, superficial punctate keratitis)
 - Keratoconus
 - Diabetic neuropathy/retinopathy (> mild nonproliferative diabetic retinopathy)
 - Cytomegalovirus retinitis
 - Color blindness (any color deficiency)
 - Diabetic macular edema (evidence of fluid)
 - Amblyopia
 - Chronic or acute uveitis (cells and/or flare in anterior chamber)
 - Strabismus (exotropia, esotropia, and hypertropia)
 - Abnormal astigmatism (mild to severe, > 5 diopters)
 - Macular hole

- 6. Eye surgery within the last 12 months (including Lasik or lens replacement)
- 7. Subject does not have the physical dexterity to properly operate the EyeQue VisionCheck device or the EyeQue app on the smartphone in the investigator's opinion

Investigational device and mode of administration: The investigational device is the EyeQue VisionCheck, and the intended use is to measure the refractive error of the eye. This is a self-administered, portable, monocular refraction system consisting of 3 main components: a mobile app, a cloud-based processing platform, and the VisionCheck optical device that attaches to a compatible smartphone owned/operated by the end user. The EyeQue app guides the subject through interactive measurements with the EyeQue VisionCheck device in order to determine refractive error.

Study duration: The study duration for each subject will be 1 day. All study-related procedures, including screening, will be completed in 1 visit.

Reference devices and mode of administration: The reference devices will be the phoropter and autorefractor. Prior to enrollment of study subjects, both devices will be calibrated following standard practice. Standard device methodology for refraction tests will be used to obtain refraction values with each device.

Criteria for evaluation:

Efficacy:

Primary Endpoint:

• Statistical non-inferiority of EyeQue VisionCheck compared with phoropter assessed by BCVA (OD, OS, and OU) measured using trial lens frames that correct the refractive error measured by each device analyzed with age stratum 45 through 65 years.

Secondary Endpoints:

- Comparison of raw refraction values produced using the EyeQue VisionCheck and the phoropter analyzed with age strata 30 through 65 years and 45 through 65 years.
- Statistical non-inferiority of EyeQue VisionCheck compared with autorefractor assessed by BCVA (OD, OS, and OU) measured using trial lens frames that correct the refractive error measured by each device analyzed with age strata 30 through 65 years and 45 through 65 years.
- Comparison of raw refraction values produced using the EyeQue VisionCheck and the autorefractor analyzed with age strata 30 through 65 and 45 through 65 years.
- Statistical non-inferiority of EyeQue VisionCheck compared with phoropter assessed by BCVA (OD, OS, and OU) measured using trial lens frames that correct the refractive error measured by each device analyzed with the age stratum 30 through 65 years.

Exploratory Endpoint:

• Subject preference of trial lens frames that correct the refractive error measured by

each of the 3 devices: EyeQue VisionCheck, phoropter, and autorefractor.

Safety:

If any AEs occur during the study, the safety endpoints will include the frequency and severity of AEs, ADEs, and serious adverse events (SAEs).

Statistics:

Analysis Populations

Modified Intent to Treat Population: All subjects that perform BCVA for trial frames with test lenses based on both phoropter and EyeQue VisionCheck.

Safety Population: All subjects that meet the screening criteria and are enrolled in the study.

After enrollment in this study was initiated, a software error was identified in the EyeQue app used with the EyeQue VisionCheck. The error was corrected and the algorithm for the EyeQue app was updated. An initial cohort of 39 subjects was enrolled in the study prior to these changes being implemented. Due to these EyeQue app updates, this initial cohort of 39 subjects will be excluded from the analysis populations and any safety information for these subjects will be listed separately.

Power and Sample Size

Approximately 200 subjects will be enrolled in this study to achieve a minimum of 100 evaluable subjects to assess the effectiveness and safety of the EyeQue VisionCheck. The initial cohort included 39 subjects; therefore, approximately 160 additional subjects will be enrolled in the study. Based on prior study data, rejection of non-inferiority bounds of 0.1 LogMAR (one line) and 0.05 LogMAR (one-half line) would require approximately 10 and 40 subjects, respectively, with 90% power on the BCVA from the resulting lens from each approach. This assumes the devices are roughly equivalent and the standard deviation (SD) is 0.077; these data are based on a previous version of the EyeQue VisionCheck device tested against an autorefractor. The proposed sample size has been inflated to allow for the possibility that a larger standard deviation will be observed in the current study, as well as to allow for comparisons within each stratum.

When the software error in the EyeQue app was identified, the algorithm for the EyeQue app was updated with more stringent parameters which may also impact the number of evaluable subjects. Due to the updates to the parameters, there may be additional subjects for which EyeQue VisionCheck refraction values are not produced, leading to an increase in the number of subjects that will not be evaluated for the primary endpoint. Of the approximately 160 additional subjects that will be enrolled in the study, it is anticipated that approximately 60 subjects will not be evaluable due to failing screening or not having refraction values produced with the EyeQue VisionCheck. Additionally, the larger sample size provides a sufficiently robust database for investigations of the secondary outcomes and descriptions of the EyeQue VisionCheck's performance characteristics.

Efficacy Analysis

Best corrected visual acuity will be assessed independently for each eye and the worse value for

Version 3.0 (17 June 2019)

each test lens set and subject will be selected for the primary analysis. Each subject's BCVA LogMAR score from the phoropter-based lenses will be subtracted from the BCVA LogMAR score from the EyeQue VisionCheck-based lenses. The mean, SD, and two-sided 95% confidence interval (CI) will be reported across all subjects for worst eye, OD, OS, and OU, and if the upper bound (one-sided 95% CI) does not include the value 0.1 for the worst eye comparison, then non-inferiority will be declared. This will be repeated using BCVA scores from the autorefractor-based lenses and EyeQue VisionCheck-based lenses.

Raw refraction values for the phoropter and EyeQue VisionCheck will be plotted and Pearson correlations calculated. This will be repeated using autorefractor and EyeQue VisionCheck values.

Subject preference data will be tabulated with counts and percentages of subjects that considered the EyeQue VisionCheck trial lenses better as well as the counts and percentages of subjects that considered the EyeQue VisionCheck trial lenses better or equal.

Analyses will be repeated for each age stratum including ages 30 through 65 and ages 45 through 65.

Safety Analyses

Adverse events, ADEs, and SAEs will be reported with counts and percentages. Adverse events that can be associated with a particular device will be reported separately from those without clear attribution. A subject experiencing more than 1 instance of an event will be counted only once for that event. Analyses will be repeated for each age stratum including ages 30 through 65 and ages 45 through 65.

4. LIST OF ABBREVIATIONS AND DEFINITIONS OF TERMS

| Abbreviation | Explanation | |
|--------------|--|--|
| AE | adverse event | |
| ADE | adverse device effect | |
| app | application | |
| BCVA | best corrected visual acuity | |
| CFR | Code of Federal Regulations | |
| CI | confidence interval | |
| eCRF | electronic case report form | |
| EDC | electronic data capture | |
| ETDRS | Early Treatment Diabetic Retinopathy Study | |
| EyeQue | EyeQue Corporation | |
| GCP | Good Clinical Practice | |
| ICF | informed consent form | |
| ICH | International Conference on Harmonisation | |
| IEC | independent ethics committee | |
| IRB | institutional review board | |
| LogMAR | logarithm of the minimum angle of resolution | |
| OD | oculus dexter (right eye) | |
| OS | oculus sinister (left eye) | |
| OU | oculus uterque (both eyes) | |
| PHI | protected health information | |
| SAE | serious adverse event | |
| UADE | unanticipated adverse device effect | |
| US | United States | |

5. INTRODUCTION

Uncorrected refractive errors account for more than 40% of the major causes for visual impairment globally (Pascolini D, 2010; World Health Organization, Blindness and vision impairment fact sheet). The most common types of refractive errors include myopia, hyperopia, presbyopia, and astigmatism. When an individual has an uncorrected refractive error, symptoms may include blurred vision, double vision, haziness, squinting, headaches, and eye strain. Refractive error correction is accomplished through the use of eye glasses, contacts, or refractive surgery. Traditionally, refraction measurements are conducted by an eye care professional during a comprehensive eye exam using diagnostic devices such as a phoropter or autorefractor. However, not all of the population has access to optometrists/ophthalmologists and these diagnostic devices or can afford these exams. Additionally, for some instances it may be more convenient to be able to obtain refraction values outside of the clinic.

The EyeQue Corporation (EyeQue) is developing an inexpensive, portable, self-administered device to measure refraction values that can be used outside of the clinic. The EyeQue VisionCheck device is a monocular refraction system consisting of 3 components: a mobile application (app), a cloud-based processing platform, and the VisionCheck optical device that attaches to a compatible smartphone owned/operated by the end user. The EyeQue app guides the subject through interactive measurements with the EyeQue VisionCheck device in order to determine refractive error.

This is a single center, clinical evaluation study to evaluate the performance of the EyeQue VisionCheck device compared with standard eye care diagnostic devices of phoropter and autorefractor in measuring refractive error of the eye. The intent of this study is to determine whether EyeQue VisionCheck is statistically non-inferior to the phoropter and autorefractor in correcting visual refractive errors. The best corrected visual acuity (BCVA) using trial lens frames prepared using refraction values from each of the 3 devices, raw refraction values from each device, and subject satisfaction with the 3 different trial lens frames will be assessed during the study.

6. STUDY OBJECTIVES

6.1. **Primary Objective**

The primary objective of this study is to determine whether EyeQue VisionCheck is statistically non-inferior to the phoropter as assessed by BCVA for each eye independently measured using trial lens frames that correct the refractive error measured by each device, for the age stratum 45 through 65 years.

6.2. Secondary Objectives

The secondary objectives include:

- Assessing similarity of refraction values (sphere, cylinder, axis) from the EyeQue VisionCheck compared with the phoropter through comparative plots and Pearson correlations
- Determining whether EyeQue VisionCheck is statistically non-inferior to the autorefractor as assessed by BCVA measured using trial lens frames that correct the refractive error measured by each device
- Assessing similarity of refraction values (sphere, cylinder, axis) from the EyeQue VisionCheck compared with the autorefractor through comparative plots and Pearson correlations
- Determining whether EyeQue VisionCheck is statistically non-inferior to the phoropter as assessed by BCVA measured using trial lens frames that correct the refractive error measured by each device, for the age stratum 30 through 65 years.

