7.3. Study Endpoints

7.3.1. Efficacy Endpoints

Primary Endpoint:

• Statistical non-inferiority of EyeQue VisionCheck compared with phoropter assessed by BCVA (OD, OS, and OU) measured using trial lens frames that correct the refractive error measured by each device analyzed with age stratum 45 through 65 years.

Secondary Endpoints:

- Comparison of raw refraction values produced using the EyeQue VisionCheck and the phoropter analyzed with age strata 30 through 65 years and 45 through 65 years.
- Statistical non-inferiority of EyeQue VisionCheck compared with autorefractor assessed by BCVA (OD, OS, and OU) measured using trial lens frames that correct the refractive error measured by each device, analyzed with age strata 30 through 65 years and 45 through 65 years.
- Comparison of raw refraction values produced using the EyeQue VisionCheck and the autorefractor analyzed with age strata 30 through 65 and 45 through 65 years.
- Statistical non-inferiority of EyeQue VisionCheck compared with phoropter assessed by BCVA (OD, OS, and OU) measured using trial lens frames that correct the refractive error measured by each device analyzed with the age stratum 30 through 65 years.

Exploratory Endpoint:

• Subject preference of trial lens frames that correct the refractive error measured by each of the 3 devices: EyeQue VisionCheck, phoropter, and autorefractor

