12.1.2. Refraction Values

Refraction values (sphere, cylinder, axis) for OD and OS will be recorded for each subject using the EyeQue VisionCheck, phoropter, and autorefractor. The refraction values will be used to prepare 3 sets of trial lens frames.

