13.3. Efficacy Analyses

Best corrected visual acuity will be assessed independently for each eye and the worse value for each test lens set and subject will be selected for the primary analysis. Each subject's BCVA LogMAR score from the phoropter-based lenses will be subtracted from the BCVA LogMAR

Version 3.0 (17 June 2019)

score from the EyeQue VisionCheck-based lenses. The mean, SD, and two-sided 95% confidence interval (CI) will be reported across all subjects for worst eye, OD, OS, and OU, and if the upper bound (one sided 95% CI) does not include the value 0.1 for the worst eye comparison, then non-inferiority will be declared. This will be repeated using BCVA scores from the autorefractor-based lenses and EyeQue VisionCheck-based lenses.

Raw refraction values for the phoropter and VisionCheck will be plotted and Pearson correlations calculated. This will be repeated using autorefractor and EyeQue VisionCheck values.

Subject preference data will be tabulated with counts and percentages of subjects that considered the EyeQue VisionCheck trial lenses better as well as the counts and percentages of subjects that considered the EyeQue VisionCheck trial lenses better or equal.

Analyses will be repeated for each age stratum including ages 30 through 65 and ages 45 through 65.

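### Pearson r is the only number planned for agreement of refraction values: it cannot show a constant dioptric bias and is not valid for raw cylinder axis

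*Combined protocol and SAP*

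**What the plan says.** The objective against the phoropter (Section 6.2) is "Assessing similarity of refraction values (sphere, cylinder, axis) from the EyeQue VisionCheck compared with the phoropter through comparative plots and Pearson correlations". The objective against the second comparator, in the synopsis and again in 6.2, has the same form: "Assessing similarity of refraction values (sphere, cylinder, axis) from the EyeQue VisionCheck compared with the autorefractor through comparative plots and Pearson correlations".

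The analysis text in Section 13.3 is "Raw refraction values for the phoropter and VisionCheck will be plotted and Pearson correlations calculated", followed by "This will be repeated using autorefractor and EyeQue VisionCheck values". The synopsis matches it. The type of plot is not stated.

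The endpoint in Section 7.3.1 is "Comparison of raw refraction values produced using the EyeQue VisionCheck and the phoropter", to be analysed in both age strata, with no metric named. On the data themselves, Section 12.1.2 says "Refraction values (sphere, cylinder, axis) for OD and OS will be recorded for each subject using the EyeQue VisionCheck, phoropter, and autorefractor". No transformation of cylinder and axis appears anywhere.

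For BCVA, by contrast, Section 13.3 takes the paired difference and states "The mean, SD, and two-sided 95% confidence interval (CI) will be reported across all subjects for worst eye, OD, OS, and OU". Nothing equivalent is planned for the refraction values.

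**The concern.** The objective is similarity, but r measures linear association. There are two separate faults.

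- **Sphere and cylinder: incomplete.** Adding a constant to every VisionCheck reading leaves r unchanged, so r carries no information about systematic bias. It also rises with the spread of the sample, and Section 8.2 admits sphere from -10 to +8. A near-perfect r for sphere could sit beside a sizeable constant offset. A plot may let the reader see a shift, but the plan calls for no estimate of it and no interval.
- **Axis: invalid.** Axis has a period of 180 degrees and is undefined when cylinder is zero. Two readings just either side of the 0/180 line describe almost the same lens, yet they enter r as nearly 180 degrees apart. A few such pairs can pull r well down although the devices agree. A raw axis plot has the same wrap-around.

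The intended use of VisionCheck (Section 9.1) is to measure refractive error. Under the plan, the size of any dioptric bias against either comparator would not be reported, and the axis coefficient would depend on where subjects' axes happen to lie.

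**Working it through.** The documents give no target r, agreement limit or sample size for the refraction comparison, so there is no planned figure to reproduce. They also give no distribution for sphere or axis. The distributions below are assumptions; the invariance of r and the 180-degree period are not.

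**Sample sizes.** n = 100 is the minimum evaluable number (Section 13.1). n = 65 is 65% of 100 for the 45-65 stratum. It is an assumption, because the 65% target in Section 7.2 applies to enrolled, not evaluable, subjects.

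**1. Sphere: effect of a constant bias**

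Let the comparator reading be X with between-subject SD s, and the VisionCheck reading Y = X + b + e, with SD(e) = 0.5 D. Then

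r = s / sqrt(s² + 0.25), which does not contain b.

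- s = 2 D: r = 2 / sqrt(4.25) = 0.970
- s = 3 D: r = 3 / sqrt(9.25) = 0.986

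These values are the same for b = 0, 0.5 and 1.0 D. The mean difference estimates b directly, with 95% CI half-width t(0.975, n-1) × 0.5 / sqrt(n):

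- n = 65: 0.124 D
- n = 100: 0.099 D

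A second simulation (n = 100, s = 2.5 D, error SD 0.4 D) gave:

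| Bias (D) | Pearson r | Mean difference (D) | Lin's concordance |
|---|---|---|---|
| 0 | 0.987 | 0.00 | 0.987 |
| 0.5 | 0.987 | 0.50 | 0.967 |
| 1.0 | 0.987 | 1.00 | 0.913 |
| 2.0 | 0.987 | 2.00 | 0.744 |

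**2. Axis: wrap-around**

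True separation = min(d, 180 - d), where d is the absolute difference of the raw values. For 1 and 179: min(178, 2) = 2 degrees.

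A constructed example of six pairs is (1,179), (2,178), (178,2), (179,1), (3,177), (177,3). The true separations are 2, 4, 4, 2, 6 and 6 degrees, and r on the raw values is -1.0.

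Large-sample r (2,000,000 simulated pairs per cell; second device = first + normal error, modulo 180; clustered axes have SD 15 degrees):

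| Error SD | Mean absolute error | Axes near 90 | Uniform axes | Axes near 180 |
|---|---|---|---|---|
| 5 degrees | 4.0 degrees | 0.95 | 0.87 | 0.75 |
| 10 degrees | 8.0 degrees | 0.83 | 0.75 | 0.55 |

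Checks by formula:

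- Near 90 there is essentially no wrap-around, so r = 15 / sqrt(225 + 25) = 0.949 and 15 / sqrt(225 + 100) = 0.832.
- For uniform axes the variance is 180² / 12 = 2,700 and r = 1 - E(D²) / 5,400, where D is the raw difference. A pair with error e straddles the line with probability |e| / 180, and its raw difference is then 180 - |e|. This gives E(D²) = σ² + 180·E|e| - 2σ², with E|e| = 0.798σ.
  - σ = 5: 25 + 718 - 50 = 693, so r = 0.87.
  - σ = 10: 100 + 1,436 - 200 = 1,336, so r = 0.75.

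**3. Stability of r for axis**

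With uniform axes and 5-degree error, 3.99 / 180 = 2.2% of pairs straddle the line. The central 95% range of r over 8,000 simulated studies was:

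- uniform axes, n = 65: 0.65 to 0.996
- uniform axes, n = 100: 0.70 to 0.996
- axes near 90, n = 65: 0.92 to 0.97

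For uniform axes, r therefore depends largely on how many pairs happen to straddle the line.

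**4. Sensitivity to the assumed axis spread**

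With axis SD 10 instead of 15 degrees (n = 100, mean over 2,000 studies), r near 90 and near 180 is 0.89 and 0.66 for 5-degree error, and 0.71 and 0.45 for 10-degree error.

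**The case against.** The strongest reply is that this is a descriptive secondary comparison. No threshold hangs on r, and no declaration changes. The consequence of a wrong prescription is tested separately, because each trial frame is made from one device's values and assessed for BCVA. The raw values are recorded, so difference summaries could be added at reporting without loss. All of this is true, and it limits the point to how agreement is described.

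It can also be said that r for sphere and cylinder is a correct description of association, accompanied by plots, and that a difference plot annotated with its mean would give an estimate of bias. The first part stands: for sphere and cylinder the analysis is incomplete, not invalid. The second depends on a plot the plan does not specify. Plotting raw values suggests a scatter plot, and no mean difference is called for.

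Finally, the axis figures rest on assumed distributions, and part of the variation in r comes from range restriction. With axis SD 10 and 10-degree error, r near 90 (0.71, no wrap-around) is below r for uniform axes (0.75). That is fair. Only near 90 against near 180 at equal spread isolates the wrap-around. That contrast remains large in all four cases: 0.95 v 0.75, 0.83 v 0.55, 0.89 v 0.66 and 0.71 v 0.45.

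**Conclusion.** The point holds. Followed as written, the plan yields an invalid statistic for axis and no estimate of dioptric bias for sphere or cylinder, against either comparator.

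For sphere, an offset of 1.0 D would leave r exactly where it was, while a mean difference would locate that offset to within about 0.12 D (n = 65) or 0.10 D (n = 100) if the difference SD is 0.5 D. For axis, wrap-around alone lowers r by 0.20 to 0.28 between clusters near 90 and near 180 in the SD-15 scenarios (0.95 - 0.75; 0.83 - 0.55), with the same true error. These sizes depend on the assumed spreads and errors. The two underlying facts, that r ignores a shift and that axis has a 180-degree period, do not.

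The primary analysis and the other BCVA non-inferiority comparisons are unaffected. The plan should be changed because the reported description of agreement could mislead in either direction: too favourable for sphere, too unfavourable for axis.

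**What to change.** Amend the synopsis, Section 6.2 and Section 13.3.

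1. Drop Pearson r, and the raw scatter plot, for axis.
2. Convert each prescription (sphere S, cylinder C, axis a) to M = S + C/2, J0 = -(C/2)cos(2a) and J45 = -(C/2)sin(2a), with J0 = J45 = 0 when C = 0. This removes both the wrap-around and the undefined axis.
3. For each comparator, age stratum and eye (OD and OS separately), report the mean difference with 95% CI, the SD of the differences and the 95% limits of agreement, with Bland-Altman plots.
4. A simpler alternative is acceptable: put all prescriptions in the same cylinder sign, give the same difference summaries for sphere and cylinder, and report the angular difference for axis on the 180-degree scale (-90 to +90). State how many eyes have no defined axis.
5. Pearson r may stay as a supplementary description of sphere, cylinder or M.

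The endpoint wording in Section 7.3.1 can stand, since all these quantities are computed from the recorded values; a cross-reference to 13.3 would make the metric explicit. The cost is protocol and SAP wording plus routine programming on data already collected under Section 12.1.2.
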